- Time period: Each experiment will include 3 months of data before each strategy is introduced and 3 months after each strategy is introduced
- Sample size (facilities): There will be 4 experiments, each will include 4 intervention facilities (16 facilities) and the same 4 comparator facilities; for a total of 20 facilities.
- Sample size (participants): We will observe 200 clients per clinic per experiment. We will collect survey data from 240 clients and 20 HCW per clinic per experiment. We will abstract register data during each experiment; while we are unable to predict total number of records to be abstracted, we expect abstraction of ~200 clients per month per clinic.
- Assumptions: α=0.05, two-sided tests, a conservative harmonic mean of 100 women presenting to ANC per month (~600 women over 6 months) per cluster (mean in PrIYA sites was ~163 per month), and a conservative estimate of the coefficient of variation of 0.5. We assume that penetration of PrEP screening and counselling is 68% (SD: 18%), time spent by HCW on PrEP services is 18 minutes (SD: 8 minutes) per PrEP initiator and 13 minutes (SD: 6 minutes) per PrEP-non-initiator, uptake is 10.5% (SD: 5%), and that knowledge and satisfaction scores are on a 100-point scale and have an SD of 20.

- Detectable effect size: We will be able to detect an absolute change of +/-4.8% for outcomes of penetration of PrEP screening, an absolute change of +/- 2 minutes in time, an absolute change of +/1% in PrEP uptake, and an absolute difference of 4 points in knowledge and satisfaction scores.
- Power: We will have at least 80% power

12.3.5) RECRUITMENT PROCEDURES

Register abstraction: We will not actively recruit individual participants for register abstraction.

Client observation: Women receiving MCH services will be approached as they enter the facility and asked to carry a time card. Each time card will collect the time that each service starts and ends and will be filled by providers, but will not collect any identifying information. Study staff will be posted at each facility until the sample size is reached.

Surveys with clients: Women receiving MCH services will be approached as they exit the facility and asked to participate in a brief survey. Study staff will be posted at each facility until the sample size is reached.

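### A 1-point change in PrEP uptake is not detectable with 80% power: as a yes/no outcome, one experiment has about 9–21% power under the planned comparisons, before clustering or trend

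*Combined protocol and SAP*

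**What the plan says.** Section 12.3.4 sets two-sided α at 0.05 and power at 80% or more. Each experiment has 4 intervention and 4 comparator facilities, with three months before and three months after the strategy starts. The inputs and claims that matter here are:

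- Uptake: "uptake is 10.5% (SD: 5"%), with a stated detectable effect of "an absolute change of +/1% in PrEP uptake". I read this as plus or minus one percentage point; a hyphen seems to be missing.
- Volume: "a conservative harmonic mean of 100 women presenting to ANC per month (~600 women over 6 months) per cluster". The same section gives about 163 per month as the mean at earlier project sites and expects about 200 abstracted records per month per clinic.
- Variation: "a conservative estimate of the coefficient of variation of 0.5". The section does not say what this coefficient describes, and gives no intracluster correlation.
- For comparison, "knowledge and satisfaction scores are on a 100-point scale and have an SD of 20", with "an absolute difference of 4 points in knowledge and satisfaction scores"; and "penetration of PrEP screening and counselling is 68% (SD: 18"%), with "an absolute change of +/-4.8% for outcomes of penetration of PrEP screening".

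The section names the software but shows no formula. It does not say whether the 5% SD refers to women or to facilities. It says estimation will use individual rather than aggregated data. Section 12.3.9 defines uptake as acceptance among women offered PrEP. The planned analyses in section 12.3.6 compare baseline with intervention periods, and intervention with comparison facilities.

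**The concern.** One percentage point on a 10.5% baseline is a very small difference for a comparison of a few thousand yes/no records. An SD of 5 points cannot describe one woman's outcome: at 10.5%, a yes/no variable has an SD of about 31 points. If the 5% entered the calculation as a woman-level SD, the detectable change is understated about sixfold.

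Uptake is one of four outcomes named in the planned interrupted time series analysis, and one of the few given a detectable effect. A reader would take 1 point as within reach. A null result for a strategy could then be read as ruling out rises of 2 or 3 points, when the experiment had a fair chance of missing them.

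**Working it through.** **Inputs (sections 12.3.1, 12.3.4).** α = 0.05 two-sided and 80% power, so z = 1.960 + 0.842 = 2.802. Baseline p0 = 0.105; p1 = 0.115 (rise) or 0.095 (fall). Women per period in four intervention facilities over three months: 4 × 3 × 100 = 1,200; 4 × 3 × 163 = 1,956; 4 × 3 × 200 = 2,400.

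**1. Reproducing the stated 1 point.** The two-means formula with SD 5 points gives n = 2 × (2.802 × 5 / 1)² = 393 per group after rounding up. With 400 per group (4 facilities × 100 women) the detectable change is 2.802 × 5 × √(2/400) = 0.99 points, and power for 1 point is 80.7%. With SD 20 the same n gives 3.96 points, against the stated 4 for knowledge and satisfaction.

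This route is an inference. The plan does not give 400 as the group size for uptake, and it equals only one month of women. The same n gives 3.57 points for penetration (stated 4.8), and 1.6 and 1.2 minutes for time (stated 2). Any larger n with SD 5 also satisfies the claim; 1,200 per group gives 0.57 points.

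**2. The SD of a yes/no outcome.** √(0.105 × 0.895) = 0.307, or 30.7 points. With 400 per group and this SD, power for 1 point is 7.5%. The ratio 5/10.5 = 0.48 is close to the stated coefficient of variation of 0.5. That suggests, but does not prove, that 5% describes variation between facilities. (For penetration, 18/68 = 0.26.)

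**3. Women needed per period.** n = 2.802² × (p0q0 + p1q1) / 0.01²

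- Rise to 11.5%: p0q0 + p1q1 = 0.0940 + 0.1018 = 0.1958, so n = 15,364.
- Fall to 9.5%: 0.0940 + 0.0860 = 0.1800, so n = 14,124.

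This is about 6 to 13 times the 1,200–2,400 available.

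**4. Power for 1 point in one experiment, ignoring clustering and trend.** Before/after: SE = √[(p0q0 + p1q1)/n]. Against the comparator (difference of the two before/after changes): SE = √[(3p0q0 + p1q1)/n].

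| Women per period | Before/after, rise / fall | Against comparator, rise / fall |
|---|---|---|
| 1,200 | 12.3% / 12.9% | 8.7% / 8.8% |
| 1,956 | 17.0% / 18.1% | 11.0% / 11.3% |
| 2,400 | 19.8% / 21.1% | 12.4% / 12.7% |

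Simulation with 200,000 runs at 1,200 and 2,400 agrees to within 0.2 percentage points.

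**5. Rise detectable with 80% power, on the same basis.**

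| Women per period | Before/after | Against comparator |
|---|---|---|
| 1,200 | 3.76 points | 5.21 points |
| 1,956 | 2.90 points | 4.04 points |
| 2,400 | 2.61 points | 3.63 points |

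**6. Power for larger rises (at 1,200 / 1,956 / 2,400 per period).**

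| Rise | Before/after | Against comparator |
|---|---|---|
| 2 points | 34 / 50 / 58% | 20 / 29 / 35% |
| 3 points | 62 / 82 / 89% | 38 / 56 / 64% |
| 4 points | 84 / 97 / 99% | 59 / 79 / 87% |

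**7. Other readings, for 1 point.**

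- Intervention-period records against all other records in the experiment (1:3): 15–18% at 100 per month, 26–30% at 200.
- 4 against 4 facilities over six months at 200 per month (4,800 per group): 35–37%.
- The same comparison with 5 points as the between-facility SD: SE = √[2 × (0.05² + 0.0940/1,200)/4] = 3.6 points. Power is 5.9%, and about 10 points (2.802 × 3.6) are detectable.
- All four experiments pooled, intervention-period records against every unexposed record, facilities ignored: 77–81% at 200 per month, 48–52% at the stated 100.

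**The case against.** The strongest reply is that the mechanism is not established. No formula is printed, and treating the SD as woman-level reproduces the uptake and score figures but not penetration or time. Penetration may even have been calculated as a proportion: 4.8 points from 68% needs 1,416 (rise) or 1,534 (fall) women per period, inside the 1,200–2,400 available. This stands, and the source of the 1 point remains an inference. The power figures do not depend on it, because they use only the stated baseline, effect, α and volumes.

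A second reply is that other contrasts give more than 21%. They do, up to 35–37% within one experiment, but none approaches 80%. Pooling all four experiments does so only at 200 per month. It also runs against section 16, which says the design is meant to isolate each strategy's own effect.

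Third, the denominator is unsettled. Section 12.3.9 counts women offered PrEP, section 12.3.6 lists a count of initiators, and section 12.3.4 does not say what the 10.5% is a share of. The figures above count all attendees. Restricting to women offered PrEP would lower power: if 68% were offered, an assumption borrowed from the screening figure, before/after power would be about 10–16%.

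Finally, the consequence is limited. Aim 2 is described as a pilot and evaluation, no stated primary outcome or decision rule rests on this figure, and all eligible records are abstracted anyway. That bears on severity, not on whether the statement is right.

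**Conclusion.** The concern holds. With uptake as a yes/no outcome on individual records, one experiment has 12–21% power before/after and 9–13% against the comparator for a 1-point change, not 80% or more. The detectable rise at 80% power is 2.6–3.8 points before/after and 3.6–5.2 points against the comparator.

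These are best-case bounds. They assume 100 to 200 women per facility per month, all counted in the denominator, independent records and no time trend. The plan gives no number of women offered PrEP and no intracluster correlation, so the true figures cannot be fixed from it; they would be less favourable. The gap concerns small changes: a 4-point rise has 84–99% power before/after and 59–87% against the comparator on the same basis. This should be fixed, but it does not invalidate the design.

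**What to change.** In section 12.3.4, replace the 1% figure with a detectable change recalculated for a binary outcome under the planned interrupted time series analysis. State the denominator (women offered PrEP, with an expected number), the allowance for clustering and time trend, and the role of the comparator facilities. Print the formula. Say whether the 5% SD refers to women or facilities; if it is between-facility variation, label it so and use it as the clustering input. Add a sentence that a single experiment is not powered for a 1-point change in uptake. The bounds given here should not be used as replacement values.

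The cost is one recalculation and a less favourable stated figure. No participants, records or facilities need be added.

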12.3.6 ENROLLMENT & STUDY PROCEDURES

Register abstraction

Consent: Individual patients will not be asked to provide consent as abstracted data are anonymous and it would not be feasible to contact clients to seek consent.

Procedures: We will abstract anonymous patient level count data from health registers at all of the intervention and comparator facilities. We will abstract the following count data from registers: women screened for PrEP interest (penetration), women offered HIV testing and PrEP (fidelity), women who initiate PrEP (uptake), women who adhere to PrEP (adherence determined via pill count), and women who refill PrEP (continuation).

Client observation

Consent: Individual patients will be given the opportunity to verbally accept or decline to carry cards; data are anonymous.

Procedures: A trained research assistant will conduct flow mapping (physical walk throughs to graphically represent patient flow pathways in a facility) and conduct time-and-motion data collection (counting minutes spent waiting and receiving various services) to describe the flow of women within health facilities and between providers as they receive services. Individual patients will be given the opportunity to carry a single sheet of paper with a study identification number to each service delivery point. Health care workers or research assistants will note the time that services begin and end. We will characterize the following outcomes: efficiency and time spent by HCW and clients.

Surveys with clients

Consent: Women will be given the opportunity to provide oral informed consent for participation or to decline participation; these surveys are anonymous.

Procedures: Women will complete a survey following service delivery completion. The following data will be collected via survey: client satisfaction with services, client PrEP knowledge, client perception of being offered PrEP services.

SARA Surveys with HCW

Consent: HCW will be given the opportunity to provide oral informed consent for participation or to decline participation; these surveys are anonymous.

Procedures: HCW will complete a survey. The following data will be collected via survey: HCW satisfaction with training and service delivery modifications.

Planned Analyses: We will use interrupted time series methodology to compare changes in penetration (PrEP screening), uptake (PrEP initiation), adherence, and continuation (PrEP refills) between the baseline and intervention periods for intervention facilities and with the comparison facilities.

12.3.7) LABORATORY METHODS

Not applicable

12.3.8) DATA COLLECTION INSTRUMENTS

- Exit Survey
- Record abstraction form

12.3.9) VARIABLES: Outcomes, indicators, and source documents

Outcome	Indicator	Source documents
PrEP penetration	Proportion of women who are screened for PrEP / total women receiving antenatal or postnatal services	Routine program data; PrEP register, antenatal register, postnatal register, family planning register
PrEP fidelity	Proportion of women who receive all PrEP specific steps in a visit: HIV testing, HIV risk screening, PrEP counseling	Primary data of anonymous exit survey assessing services received Direct observation of client-provider interactions
		Routine program data: HIV testing register, PrEP register, antenatal register, postnatal register, family planning register
PrEP uptake	Proportion of women who accept PrEP among those offered	Routine program data: PrEP register
PrEP continuation	Proportion of women who present for a refill among those initially prescribed PrEP	Routine program data: PrEP register, pharmacy records
PrEP adherence	Proportion of women who have >80% adherence to PrEP by pill count among those initially prescribed PrEP	Routine program data: PrEP register, pharmacy records
PrEP efficiency	Patient flow mapping to identify more efficient client flows with fewer transitions between physical spaces and providers	Primary data collection through direct observation of patient flow
Timeliness	Time and motion data to assess wait times, service delivery times, and HCW burden	Primary data collection through direct observation and time collection
Client satisfaction	Satisfaction on a scale of 1-10 adapted from Training Satisfaction Survey	Primary data collection through anonymous surveys
HCW satisfaction	Satisfaction on a scale of 1-10 adapted from Training Satisfaction Survey	Primary data collection through anonymous surveys
Client PrEP knowledge	10 questions based on content covered in counseling sessions	Primary data collection through anonymous surveys

12.3.10) TRAINING PROCEDURES

[name] will oversee training of study staff on PrEP optimization procedures, exit surveys, and record abstraction. Trained study staff will work with facility staff at all facilities to ensure appropriate implementation of ITS-specific PrEP optimization procedures.

12.3.11) STUDY MATERIALS

• Oral consent guide

12.4 AIM 3:

To review evidence, findings, and understanding of study findings through two stakeholder workshops and to evaluate these workshops through IDIs and surveys.

	Aim 3 Stakeholder views on research findings and best practices					
Population	PrEP policymakers, implementers, frontline HCW, PrEP ambassadors, community advisory board members					
Design	Qualitative cross-sectional design					
Data collection	IDI, facilitated workshops					
Sample size	PrEP policymakers: up to 15 IDIs					
	Workshop participants: up to 50 participants					
Outcome(s) of interest	Decision-making process and understanding of budget impact analyses, consensus-determined best practices for PrEP delivery and integration					
Inclusion	PrEP policymakers and implementers: involved in making decisions related to PrEP at national or county level, >18 years					
ontonia	Other stakeholders: stakeholder in in PrEP delivery, 218 years; adolescent PrEP ambassadors, 215 years					
Exclusion criteria	N/A					

12.4.1) STUDY DESIGN

PrEP policy makers, implementers, and other stakeholders will be invited to participate in a series of workshops aimed at identifying priority interventions to test for PrEP optimization, review findings of the interrupted time series intervention testing, draft a document of best practices for PrEP implementation, and review budget impact analyses. At the final workshop, cognitive interviews will be conducted with stakeholders to understand how they interpret and understand the budget impact analysis.

12.4.2) STUDY POPULATIONS

Stakeholder meeting to develop best practices

PrEP policy makers, implementers, and other stakeholders will be identified through consultation with national and county level ministry of health officials. We will ensure that each workshop includes up to 50 participants representing a range of stakeholder perspectives and experiences, at least:

- 5 national level policy makers
- 5 county level policy makers
- 5 facility level policy makers

In aligning with core principles of community engagement and ensuring voices of all key stakeholders are represented, including potential end users and those within the community of practice [62], we will purposively invite adolescent PrEP ambassadors, frontline HCWs, implementing partner organizations, representatives from the National AIDS and STD Control Program (NASCOP), and County health officials to participate in the Best Practices Development Workshop. Representatives from stakeholder groups will be identified through informal discussions with MOH and County Health officials, Community Advisory Board members, PrEP implementers and peer-reviewed published articles or presentations from local, regional or international conferences.

12.4.3) SAMPLE SIZE DETERMINATION AND FORMULAS USED

Stakeholder meetings to develop best practices:

We will conduct 1 workshop with up to 50 participants representing a range of stakeholder perspectives and experiences. Based on a previous workshop conducted in this region with diverse stakeholders from various cadres who engaged with formative research materials, this number of participants is sufficient to reflect a range of experiences and priorities, but small enough to facilitate crucial interactive activities; we predict that this sample size will additionally be sufficient to reach theoretical saturation, that no new themes are identified with each additional individual.

Budget impact analysis review:

We will conduct a series of 15 semi-structured, in-depth interviews with policymakers. Based on previous studies in this region, we predict that 15 IDIs will be sufficient to reach theoretical saturation, that no new themes are identified with each additional IDI [59].

12.4.4) RECRUITMENT PROCEDURES

We will conduct a working meeting with an estimated 50 selected HCWs and policy makers from throughout Kenya with expertise PrEP delivery and MCH services. HCWs with significant experience in assisting PrEP delivery and/or MCH services will be purposively recruited from high performing clinics from Aims 1 and 2. We will also recruit healthcare workers known for their work in PrEP and MCH through reviewing peer-reviewed published articles or presentations at scientific meetings.

HCWs and policy makers participating in the working group will be purposively selected and contacted by phone, email or in person by study staff. They will be told the details of the working group, including its purpose and scope of work. A script outlining talking points used for recruitment is attached as an appendix. Those willing and eligible to participate will be asked to give written consent to be part of the working group and have the discussions audio recorded and information about the process written up into a publishable manuscript. It will be emphasized that participation is completely voluntary and opting not to participate will have no repercussions on the HCWs employment. They will read through the consent form on their own. One of the study personnel will then go through it with them verbally and answer any questions they might have. Those who consent will participate in the workshop with study staff to refine and adapt the transition tools. All participants will provide their contact information (phone, name, email if necessary) for follow-up until the working group meeting is conducted.

12.4.5) ENROLLMENT & STUDY PROCEDURES

Stakeholder meeting to develop best practices:

Consent: Stakeholders will be invited to provide written informed consent for participation in this workshop.

Procedures: A best practices document will be developed and refined during a 2-day workshop. The workshop will be aligned with community-based participatory research and community engagement practices [63], including developing a shared vision, collaboratively identifying goals, and meeting the objective of developing trusting and sustainable relationships between all stakeholders to ensure long-lasting impact and improved health outcomes.

Data from Aims 1 and 2, as well as past learning from the PrIMA and PrIYA projects, will be compiled into brief reports synthesizing key elements of PrEP provision through MCH and FP clinics in Kenya. Reports will include information on client demographics, PrEP uptake and access experiences, challenges in PrEP delivery across ecological levels, and employed implementation strategies and identified implementation strategy domains.

The Best Practices Development Workshop will be conducted over 2 days. Aligning with previously conducted best practices and intervention development processes [64–66], the workshop will include small and large group deliberative processes designed to maximize opportunities to hear all stakeholder views. To ensure accurate portrayal of stakeholder input, all large and small group sessions will be audio recorded and reviewed during final best practices development processes. Final workshop sessions will focus on implementation planning, addressing key steps towards implementation found in the Guideline Implementation Planning Checklist [67]. We will also conduct an evaluation of the best practices development process using post-development workshop questionnaires, focusing on 3 key process outcomes: recruitment, context, and satisfaction [64].

Budget impact analysis review:

Consent: Policymakers will be invited to provide written informed consent for participation in semistructured in-depth interviews.

Procedures: During the interviews, policymakers will be asked to narrate their thoughts aloud, borrowing methodological approaches from cognitive interviewing, a technique used in psychology to assess comprehension [68].

Question guides will cover the following topic flow: 1) factors that influence policymaker's current approach to making a decision about whether or not to adopt a new intervention into their clinic/county/national program, 2) current approach to considering cost data, budget impact, and cost-effectiveness data in their decision-making. Midway through the interview, a hypothetical vignette will be introduced, in which the policymaker is asked to consider adopting PrEP delivery integrated into ANC, either with or without additional implementation strategies from Aim 2, into their clinic/county/national program. Initially, information will only be provided about effectiveness in terms of penetration of PrEP screening. The interviewer will then assess: 3) factors that influence the policymaker's initial decision about whether or not to adopt the intervention. Then the results from the budget impact analysis will be shared in printed form, supplemented by standardized explanatory scripts, and the interviewer will assess: 4) policymaker's understanding of the results, 5) any changes to policymaker's initial decision regarding adoption of PrEP provision integrated into ANC.

Planned Analyses:

Stakeholder workshop: We will use a facilitated workshop in order to identify best practices for PrEP implementation in MCH and FP settings. Key themes from the workshop with be documented and summarized into a PrEP implementation best practices report.

Budget impact analysis: We will use qualitative methods to explore policymaker approaches to decision making with limited resources.

12.4.6) LABORATORY METHODS

N/A

12.4.7) DATA COLLECTION INSTRUMENTS

- Workshop Evaluation Survey

Workshop participant demographic survey

12.4.8) TRAINING PROCEDURES

Drs. [name] and [name] will oversee the training of study staff on workshop procedures and oversee the workshop.

12.4.9) STUDY MATERIALS:

Workshop consent

- Recruitment Script
- Workshop topic domains overview

13) QUALITY ASSURANCE PROCEDURES

Adherence to protocol: Weekly reporting of enrollment, IDIs/FGDs transcript completion, and data collection will enable us to monitor that the study is running according to approved protocols. Frequent reporting will also enable us to respond quickly to any problems that arise during the study.

Data Quality: A dedicated data team will be responsible for data collection using an electronic data collection platform, RedCAP. The data team will communicate weekly with the operations team and leadership including reporting on data cleaning, study monitoring, and interim analyses.

14) ETHICAL CONSIDERATIONS 14.1 ASSESSMENT OF RISKS AND BENEFITS

) ADEQUACY OF PROTECTION AGAINST RISKS

Participants may feel discomfort in the questions they are asked during the FGDs, IDIs, and surveys. All participants will be informed that they do not have to answer any questions they do not want to answer. Additionally, there may be a breach in confidentiality of participants. We are taking all necessary precautions to prevent a breach in confidentiality, including storing materials that could identify participants in locked files, and storing all participant information in encrypted locations.

ii) POTENTIAL BENEFITS OF PROPOSED RESEARCH TO THE SUBJECTS AND OTHERS Health care workers and women clients will not directly benefit from the proposed research. PrEP policy makers and implementers may benefit from the best practices and budget impact analysis activities as it will provide information that can inform their jobs.

iii) IMPORTANCE OF THE KNOWLEDGE GAINED

Information gained through this study will result in improved PrEP delivery to women receiving MCH services, while also optimizing health care worker resources.

15) DATA MANAGEMENT AND STATISTICAL ANALYSIS PLANS

All data for this project will be managed at the Kisumu study office and the University of Washington in Seattle. Participants will be identified according to unique identification numbers—no identifying information will be captured or stored in this study, except the information needed for scheduling purposes or re-contacting to verify data accuracy. All qualitative data collected through interviews and focus groups to address Aim 1 and Aim 3 will be stored on a secure server. All recording devices will be wiped clean after recordings are uploaded to the secure server.

All quantitative data collected through surveys to address Aim 2 will also be stored on a secure server. Quantitative data collected during the course of this study will be collected electronically via REDCap data collection software. Data will be uploaded daily via REDCap Mobile App from tablets to the REDCap web server. Data will be transported via secure socket layer (SSL) and only accessible by authenticated users. Weekly reports will be generated to monitor study progress and troubleshoot problems. All computers, tablets (used for primary data collection), and individual study databases will be encrypted and password protected. Participants will be assigned a non-identifiable study code upon enrollment. Study analysts will receive only coded data. The links to patient identifiers will be retained in a password-protected file on an encrypted computer.

a) Data Ownership

The proposed project is a collaborative effort between investigators at the UW and KNH. The aforementioned institutions will jointly share ownership of the data. Study investigators at the UW and KNH will have full access to the data. Authorship on publications, conference presentations, abstracts and other materials generated from this study will reflect contribution to design, execution and analysis of the study.

b) Data Release/Sharing Policy

All quantitative data collected as part of this proposed research project will be made available to access or download files on a study related website (URL to be determined) following ERC approval for data sharing and agreement to the data sharing agreement. The data sharing agreement will ensure commitments to:

- 1. Using the data only for research purposes and without attempting to identify study participants (if applicable);
- 2. Securing the data using appropriate computer technology;
- 3. Destroying or returning the data after analyses are completed;
- 4. Restrictions on redistribution of the data to third parties; and
- 5. Proper acknowledgement of the data resource.

c) Data Monitoring Committee

Prior to study initiation, we will convene a data monitoring committee (DMC) to review study aims, statistical analysis plan, and protocol. An annual DMC will be held during Aim 2 activities will be conducted to assess interim outcomes.

16) STUDY LIMITATIONS AND HOW TO MINIMIZE THEM:

Interrupted time series designs do not have as strong protection against confounding as randomized trials. Cluster randomized trials were not feasible or reasonable at this stage of scientific discovery. We considered alternative quasi-experimental designs (classical pre-post, difference in differences, regression discontinuity, stepped wedge), but none provided as strong control for temporal trends or heterogeneity between clinics. We considered adaptive designs, but wanted to isolate the individual, rather than additive or sub-group level, impact of the implementation strategies.

We hope to gain insights on improving efficiencies for PrEP delivery in MCH and FP clinics based on views from a group of stakeholders with broad expertise. MCH and FP clinics in Kenya face unexpected events (specifically, health worker strikes and implementation of universal health care [UHC]) that may influence HCW and client views on PrEP implementation and may challenge the intervention pilot. Our team has been able to work around these challenges in the past, liaising with private sector MCH/FP clinics (during public sector strikes) and overtly addressing new challenges such as UHC as part of process of stakeholder engagement. Stock-outs of self-tests or PrEP could challenge implementation of the pre-designed HIVST model; however, we have been assured that there is sufficient supply of PrEP and HIV self-tests in Kenya and that studies such as the one we propose are of high priority nationally and regionally in Kenya for use of these commodities.

During direct observation, such as that employed for time-and-motion data collection, there is the possibility of the Hawthorne effect, in which individuals modify their behavior because they are observed. This is typically a concern with shorter data collection periods; these data will be collected over a series of approximately 2 weeks, so we anticipate a more limited or negligible Hawthorne effect. There is no potential benefit for the individuals being observed to modify their practices since the evaluation of is of the health system in general rather than a specific behavior.

17) TIMELINE/ TIME FRAME:

	2019	2020			2021						
	Q4	Q1	Q2	Q3	Q4	Q1	Q2	Q3	Q4	Q1	Q
Protocol development and ethics approvals											
Study start up											
Video development	х	х									
Develop training materials	х										
Train team		х									
Sensitization meetings		х									
Aim 1: Identify and quantify innovations											
Identify & sensitize facilities		х									
Qualitative data collecttion			х								
Quantitative survey completion			х								
Data analysis & manuscript development				х	х						
Aim 2: Intervention testing											
Experiment round 1				х	х						
Experiment round 2						х	х				
Experiment round 3								х	х		
Experiment round 4										Х	х
Data analysis & manuscript development											
Aim 3: Stakeholder Workshop											
Identify & recruit participants											
Hold workshop											
Analyze results and disseminate results											

18) HUMAN SUBJECTS

a) Ethical Approval

We will obtain ethical approval from the University of Washington (UW) Human Subjects Division (IRB) and Kenyatta National Hospital-University of Nairobi (KNH-UoN) Ethics and Research Committee (ERC). There will be minimal risk to the participants taking part in this study. Any changes to the protocol will be submitted to the UW IRB and KNH-UoN ERC.

b) Collaborating sites

The study will be conducted in collaboration with the UW, KNH, and NASCOP. The study will be reviewed by the KNH ERC and UW IRB and will not be started before approvals are obtained from all two organizational review boards.

c) Informed Consent

We will obtain electronic written informed consent for participation in all in-depth interviews, focus groups and HCW surveys that occur under Aim 1. The consent will explain to each potential participant the purpose, risks and benefits of the study. Participants will be informed that they can choose to withdraw from the study at any point and for any reason. They will also be informed that participation is completely voluntary. Participants will be offered a copy of the consent form to keep and will be informed that their role will end after they complete either the in-depth interview, focus group, or survey. Participants who agree to participate in study activities will sign the informed consent form using the electronic consent module through RedCap. This will allow for electronic collection of consent signatures, allowing for realtime consent quality monitoring, as well as secure, encrypted, storage of participant names and signatures. Identifying information on participants will only be collected during the informed consent process.

For exit interviews during Aim 2 activities, we are requesting a waiver of written consent. The purpose of these interviews is to assess knowledge and satisfaction for the PrEP optimization approaches. Data collectors will approach women as they exit the facility, explain the purpose of the survey, and ask whether they are willing to answer a few questions. A waiver of written consent is requested as there will be no identifying information of the participants. The guide for obtaining oral consent is included in the consent material appendix.

IDIs and surveys will be verbally administered to ensure participants who cannot read or write are still able to participate in this study.

Comprehension: Participants who do not consent in the presence of study staff (for example, prior to self-administered electronic surveys) will be given the phone number of study staff and will be encouraged to call if they have any questions about the consent or study.

Study staff will review the informed consent information with each study participant when consenting is conducted in-person. Study staff will also ask participants a 2-3 questions to assess understanding. Questions may include:

- 1. What is the purpose of this study?
- 2. When can you decide not to participate in this study?
- 3. Will we record your voice during this study?
- 4. Will we access your medical records during this study?

Waiver of written consent for data extraction

Register abstraction: For aims that involve register abstraction, we are not planning any direct contact with patients. We will exclusively abstract data from registers and medical records without abstracting any personally identifiable information or constellation of variables that could personally identify individuals. The study data clerk will review health registers and medical records and will abstract simple count data about the number of individuals who complete each step. While registers and medical records may contain personally identifiable data, study data clerks will not abstract any of these variables, nor any constellation of variables that could be

personally identifiable. We are requesting a waiver of informed consent to abstract medical records from this population.

Waiver of parental permission for 15-17 year olds

The age of majority in Kenya is 18 years. For adolescent girls, ages 15-17 years, we are requesting a waiver of parental consent for participation based on the following points:

- 1. Adolescents are able to provide consent (parental consent can be waived) for HIV and STIs testing and treatment in Kenya). However, parental involvement is always desirable and adolescents would be able to choose whether they want to have parents involved in the decision of whether or not to provide consent, and participate in the study.
- 2. If there are confidentiality issues regarding adolescents discussing personal HIV testing or sexual activity with their parents, requiring parent consent could breech confidentiality of the adolescent.
- 3. Recent Kenya Demographic Health Surveys have allowed sexually active adolescents to participate in national surveys, which allows this marginalized population to be represented and their data used to help guide public health programs and policies.
- 4. Excluding adolescents from the study would be denying them an opportunity to participate in research to improve PrEP delivery in FP and MCH clinics. Allowing adolescents the opportunity to provide their own consent is in alignment with the ethical principles of justice, beneficence, and autonomy.
- d) Handling Adverse events

We do not anticipate any significant adverse events to occur throughout this study as the goal of this study is simply to understand barriers and facilitators to PrEP adherence. However, in the event that an adverse event occurs, participants will be given contact information for study team members. All unanticipated problems will be reported to the PIs and ethics committee according to UW, KNH, and KNH ERC guidelines.

19) BUDGET (total budget period) 20) LIST OF ABBREVIATIONS 21) LIST OF APPENDICES/ATTACHMENTS

